**Non-biocompatibility risk mitigations:**

All materials used in the NuView are biocompatible. The risks surrounding biocompatibility for medical devices are well understood and the FDA has excellent [biocompatibility guidance documents](#). Similarly, there are recognized international standards surrounding biocompatibility such as [ISO 10993-1](#).

We have taken the risk of biocompatibility into account in the development of the NuView device. The device is made from 100% biocompatible materials for piece of the device. Below is a list of all materials used in the device, including any adhesives, 3D resins, or other materials

*Carbon Inc.'s Sil 30 printable resin:* The press-fit collar will be made from Carbon Inc.'s SIL 30 material which is a soft, biocompatible, silicone urethane elastomer that has undergone ISO-10993 testing for skin and mucosal membrane contact. The press-fit collar will be made from this soft, elastic, silicone urethane elastomer in order to safely interact with tissue during FAP. This soft silicone urethane elastomer (SIL 30) has undergone rigorous biocompatibility/sterility testing which makes it ideal for short term mucosal membrane contact (up to 24h in duration). See [Appendix B](#) for additional details relating to biocompatibility and sterility.

*Formlabs's Medical Grade Tough 1500 Resin:* Tough 1500 material has been tested to ISO-10993 biocompatibility standard (see [Appendix B](#)). This material currently makes up the NuView's body and backbone. It is an excellent material for the this because of it's stiff, yet pliable nature being able to bend and spring back quickly to its original shape. Similarly, this material is compatible with a wide range of common sterilization processes for medical devices. For more information on this material, including biocompatibility and sterility information please refer to [Appendix B](#).

*Mirror:* The mirror is made from 1 mm-thick mirrored glass. This component will be custom-

manufactured by Knight Optical using a scribing process. Upon delivery to EndoTheia, the mirror will be cleaned using 99% isopropyl alcohol prior to assembly.

*Adhesive info:* Loctite 435 humidity-cured ethyl-based adhesive from Henkel has been tested to ISO-10993 biocompatibility standard (see [Appendix B](#)). This adhesive is used to fasten the press-fitting feature with projections and the mirror to the structural body of the NuView. Similarly, this adhesive is compatible with a wide range of common sterilization processes for medical devices, such as cold sterilants, ethylene oxide, and gamma radiation. For more information on this material, including biocompatibility and sterility information please refer to [Appendix B](#).

***Risk summary: We have determined that because all materials used in the construction and all adhesives used during device assembly are biocompatible and have been tested to the appropriate ISO 10993 standard that the risks associated with biocompatibility are acceptable and do not pose serious risk to the health, or welfare of the subject.***

#### **Sterility risk mitigations:**

Sterilization risks are inherent to all medical devices. Both the risks associated with infection when devices are not sterilized and the risks associated with material property degradation if an inappropriate sterilization method is chosen for a given material. We have taken both of these potential risk categories into account during the development of the NuView device.

[figure not shown]
We have included information in [Appendix B](#) with regards to sterility showing how an independent sterility testing house (STERIS) has verified that autoclave is an appropriate method of sterilization of both of the Formlabs's resins we've used in the construction of the device. Similarly, the medical grade adhesive we've used during the assembly process has shown to be resilient up to temperatures much higher than those seen in the autoclaving process appropriate for the NuView ([Appendix B](#) for data on adhesive). We have also verified that this adhesive maintains its properties and functional strength sufficient post sterilization. All materials used in the construction and assembly are appropriate materials for our selected sterilization process of autoclaving and all of the materials show resilience to the autoclaving sterilization process. Please refer to [Appendix B](#) to see the resilience of selected material and the appropriateness of the autoclaving sterilization process.

***Risk summary: We have determined that the risks associated with sterility and the sterilization process are currently acceptable and do not pose serious risk to the health, or welfare of the subject.***

#### **Device breakage & failure risk mitigations:**

Another risk inherent to medical devices is the risk of device breakages or failures. Indeed, a large part of the development process is aimed at identifying and mitigating potential device breakages and failure points. Large efforts are made to identify these possible breakages through a systematic process such as Failure Modes & Effects Analysis (FMEA) and Fault Tree Analysis (FTA). As part of our development process, we employ both of these methods for identifying potential device failures and breakages. Another way device developers try to identify potential failure modes or likely breakages is to research what the failures and breakages are reported in the FDA's MAUDE database for other similar type devices. We have reviewed this MAUDE database data for device

breakages and failures for devices similar to the NuView (refer to [Appendix A](#)) and then taken this information into account during design to create risk controls to prevent similar type of failures/breakages from happening during use of the NuView device.

[figure not shown]
*Figure 4. Hairlike projections are known failure points for the Arc Endocuff and have resulted in several device breakages during use in human patients.*

One of the most commonly seen device breakages reported in the MAUDE database for distal endoscope attachment type devices is that of projection breakages. These endcaps have hairlike projections that are meant to smooth out the mucosal folds and increase endoscope visualization. These hairlike projections can be seen in the figure below. These projections are intended to fold back during endoscope insertion and then to fan outwards and interact with the mucosal tissue as you gently pull the endoscope backwards. During this interaction with the mucosal lining, they both smooth the folded tissue and also keep the tissue slightly away from the endoscope's tip so that the tissue is at the proper viewing distance from the endoscope optic or viewing lens. These hairlike projections are also prone to breaking off from the device due to their slim profile and pinpoint connections to the body of the device. For example, there were several different reports of this type of device breakage reported in the MAUDE database for the arc Endocuff device ([K151801](#)). The below table lists a few examples reports for hairlike projection breakages for the Arc Endocuff and there are links within the table to the full reports.

*Table VII. MAUDE Data (from the FDA database)*

MAUDE DATA: Example reports for hairlike projection breakages				
Device	Date	Problem	Description	Harm
K151801	12/09/2015	Detachment of device component	Device detaches from the endoscope	No harm to the patient
K151801	7/23/2015	Break; detachment of device component	Device detaches from the endoscope	No harm to the patient

*Figure 5. Risk control features implemented in the NuView device based on known failures of similar type devices as reported in the FDA's MAUDE database.*

We have taken this MUADE breakage data into account during the design and development of the NuView device by creating a risk control that ensures redundancy through the design of the projections themselves. This risk control is an added safety loop (seen in the picture below) connecting each hairlike projection so that each individual hair is no longer able to detach through a single breakage. Instead, now there needs to be at least two breakages for any one project to break off from the device and in some cases two breakages will still not be sufficient to dislodge a projection. Similarly, another risk control was to design out the thin pin-joint failure zone which we believe contributed to several of the breakages of the Arc Endocuff device and instead us a more robust and larger joint of molded flexible material.

[figure not shown]
We have also conducted verification tests related to the forces required to break these arm-like projections to gain confidence in the device's robustness. The following give examples of how strong these arm-like projections are and then we compare this strength to another FDA approved device to gain confidence that the NuView device is sufficient at resisting this type of device breakage.

**a. *Strength of Visual Enhancement web attachment:***

We have characterized the force required to detach the NuView arm-like projections (called the Visual Enhancement web). The detachment force was measured by properly affixing the NuView device to a small clamp mounted to the bottom of a force gauge and grabbing individual web projections using another clamp attached to the lever arm of the calibrated force gauge. The test setup for this experiment can be seen in the figure below.

The safety loop on the NuView device were cut to allow for the measurement of the individual web detachment forces. The top clamp was opened and the first projection was inserted and the clamp was shut. The lever was lowered and the NuView device itself was attached to the mounted clamp on the bottom of the force gauge. The force on the force gauge was set to peak tension and zeroed. The clamp was slowly pulled upwards until the

*Figure 6: Experimental setup for the removal of the NuView Visual Enhancement web*

projection became fully detached. That detachment force was recorded and the entire test setup was repeated for all eight NuView projections. Through these tests it was found that an average detachment force of **8.3 N** and minimum detachment force of **6.6 N** was required to fully detach the visual enhancement webs.

This detachment force greatly exceeds the expected forces on the NuView when deployed in the patient, giving confidence that the device will not unintentionally lose any web projections during the procedure. Additionally, 5 of the projections are equipped with a safety loop, increasing the force needed to fully detach those sections during a procedure. No device failures or breakages were observed in these experiments. During an actual procedure, we do not expect the webbed portions of the visual enhancement web to become detached from each other. This data gives confidence that the endoscope attachment press fitting is more than sufficiently robust.

*Table 8. Summary of the forces required to detach the NuView Visual Enhancement web*

Device	Average Force [N]	Min Force [N]	Max Force [N]
1	8.6	6.6	11.0
2	8.0	7.6	8.4
3	8.8	8.4	9.0
4	7.8	7.4	8.0
Overall average:	8.3	6.6	8.0

- b. ***Comparing Visual Enhancement web detachment forces to an FDA approved device:***  
 We have compared the force required to detach the Visual Enhancement Web from the NuView to an FDA approved distal endoscope attachment device similar to the NuView, called the Arc Endocuff. This is to ensure that the Visual Enhancement web is at least as safe from detachment events as the ones present on the Arc Endocuff. The detachment force was measured by attaching the Arc Endocuff to a clamp and pulling the projections off individually using a calibrated force gauge similar to how the NuView detachment forces were characterized. Through these tests, it was found that an average detachment

force of 8.5 N and minimum force of 6.20 N is required to fully detach the Arc Endocuff from the endoscope. A summary of the forces required to remove the Arc Endocuff from the endoscope can be seen in Table IX.

*Table 9. Summary of the forces required to detach the Arc Endocuff Visual Enhancement web*

Device	Average Force [N]	Min Force [N]	Max Force [N]
1	7.8	6.2	9.0
2	8.9	7.4	11.0
3	8.4	7.2	11.0
4	8.9	7.8	11.4
5	8.7	7.4	11.0
Overall average:	8.5	6.2	11.0

Each of the arm like projections that make up the NuView's enhancement web appear to be as robust as each of the arm-like projections of the FDA approved comparison device. The NuView has also included a safety loop that adds redundancy into these arm-like projections which means that no single failure can cause the projection to tear off. The FDA comparison device does not have this redundancy and yet is still considered safe.

***Risk Summary: Based on our review of the MAUDE database for device breakages and failures of similar type device to the NuView and our proposed risk controls to mitigate these known breakages, as well as our verification testing to ensure the NuView's robustness, we have determined that the risks associated with device failures and breakages are currently acceptable and do not pose serious risk to the health, or welfare of the subject.***

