Device projections breakage	Slight delay in patient care due to retrieval	We have examined the MAUDE database for device breakages for a similar type device and one of the most commonly seen device failures for this type of device is that of projection breakages (See MAUDE data in Appendix A). We have taken this into account during the design of the device and have created redundancy through the addition of a safety loop so that each projections needs at least two independent breakages for any one projection to break off from the device. Similarly, we have designed out the thin pin-joint failure zone which we believe contributes to the majority of the breakages for the Arc Endocuff device that our NuView device is designed after. Together, these activities have led us to determined that this risk has been mitigated to an acceptable level through the implemented risk controls and as such does not pose serious risk to the health, or welfare of the subject. Patients will be counseled about these risks. For more information regarding this risk please see a detailed discussion here.
Irrigation and/or illumination blockages	Slight delay in patient care	We have mitigated this risk through inherent design, having made the press fitting attachment feature such that it will only come into contact with the side profile of the endoscope and will stay securely in place without covering the front face of the endoscope where the suction and irrigation channels are located. Further we have incorporated a drainage hole located in the backbone of the device to aid in irrigation. We have also run verification tests to ensure that irrigation and/or illumination have been maintained. For more information regarding this risk please see a detailed discussion here.
Traumatic features,	Tissue trauma	We have designed the NuView using a soft, flexible, biocompatible material that should reduce tissue trauma. We

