This removal force greatly exceeds the expected forces on the NuView when deployed in the patient giving confidence that the device will not unintentionally detach during the procedure. No systemic device failures or breakages were observed in these experiments. The only nonperformance observed in these experiments was that one of the press-fit collars for a single device started to show adhesive failure on the 15th time of being reattached and unattached from the endoscope. We believe this was in part due to the experimental setup, where higher and repeated stress was placed on this seam than would be seen in clinical use where the physician would attach the device once and then remove the device once at the end of the procedure. In total, of the 120 attachment/detachments performed only one single device showed a single adhesive issue on the last of the 15 attachment/detachment runs. Of all the other devices tested, no failure was detected; this enforces the assumption that this failure was a one-off test setup or manufacturing failure. During an actual procedure, we expect the NuView to be attached once at the beginning of the procedure and then detached from the endoscope once upon completion of the procedure. This data gives confidence that the endoscope attachment press fitting is more than sufficiently robust.

*Table 5. Summary of the forces required to detach the NuView from the endoscope*

Device	Average Force [N]	Min Force [N]	Max Force [N]
1	9.46	8.72	10.23
2	9.50	9.00	10.40
3	8.22	7.92	8.65
4	10.19	9.30	11.91
5	10.10	9.56	11.65
6	9.96	8.95	10.64
7	9.54	8.69	10.20
8	10.09	9.58	10.79
Overall average:	9.64	8.97	10.56

- b. *Comparing detachment forces to an FDA approved distal endoscope attachment device:*  

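### The risk analysis credits every NuView projection with a safety loop, but the bench-test text gives the loop to only five of eight; separately, two summary cells in Tables 8 and 9 are wrong

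*Protocol*

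**What the plan says.** Four places in Protocol section 4.1 describe the safety loop.

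- Table 4, row on projection breakage: "each projections needs at least two independent breakages for any one projection to break off from the device".
- Text under device breakage and failure, describing the loop: "connecting each hairlike projection so that each individual hair is no longer able to detach through a single breakage".
- Item b, comparison with the Arc Endocuff, after Table 9: "no single failure can cause the projection to tear off".
- Item a, strength of the Visual Enhancement web: loops were cut so that projections could be pulled singly, and "the entire test setup was repeated for all eight NuView projections". The same item then says: "Additionally, 5 of the projections are equipped with a safety loop".

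Item a summarises the test as "average detachment force of 8.3 N and minimum detachment force of 6.6 N was required". Tables 8 (NuView) and 9 (Arc Endocuff) each end in a row labelled as an overall average: 8.3 / 6.6 / 8.0 N and 8.5 / 6.2 / 11.0 N for average, minimum and maximum force.

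Table 4 also says that patients will be counseled about this risk, and gives the harm as a short delay while the piece is retrieved. The procedure steps (section 3.1.6.2, step b, item 6, and section 5.6, item f) end with removal of the scope and device.

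**The concern.** Three statements say that all projections have redundancy, and one says that five do. They cannot all describe the same device. The property at issue is a risk control on which patients are to be counseled, against a failure that the protocol itself reports for the comparator. If five is correct, the risk table overstates the protection.

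Retrieval of a broken piece also presupposes that someone notices the loss, and neither version of the procedure includes a check of the device after withdrawal.

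The summary rows that support the strength argument also look inconsistent. In Table 8 the overall maximum force is printed as lower than the overall average force.

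**Working it through.** **1. Loop coverage**

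| Place in section 4.1 | Projections with redundancy |
|---|---|
| Table 4 | each |
| Text introducing the loop | each |
| Item b, after Table 9 | no single failure suffices |
| Item a | 5, with eight projections named |

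Could eight be the total number of pulls over the four devices in Table 8? A device with only two readings must have an average of (min + max)/2:

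- Device 1: (6.6 + 11.0)/2 = 8.8; stated 8.6.
- Device 2: (7.6 + 8.4)/2 = 8.0; stated 8.0.
- Device 3: (8.4 + 9.0)/2 = 8.7; stated 8.8.
- Device 4: (7.4 + 8.0)/2 = 7.7; stated 7.8.

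Devices 1, 3 and 4 therefore need at least three readings each and device 2 at least two, or 3 + 3 + 3 + 2 = 11 in all, more than eight. Eight per device is the natural reading. On that reading 8 - 5 = 3 projections per device are not stated to have a loop.

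**2. Convention for the summary row**

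Tables 5 and 6 carry the same row label. Their column means are:

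- Table 5: 77.06/8 = 9.63, 71.72/8 = 8.97, 84.47/8 = 10.56; printed "9.64 8.97 10.56". These agree apart from 0.01 in the first cell.
- Table 6: 35.54/4 = 8.89, 30.8/4 = 7.7, 43.2/4 = 10.8; printed 8.9 / 7.7 / 10.8.

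The convention there is the column mean throughout.

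**3. Tables 8 and 9**

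| Cell | Printed | Column mean | Overall extreme |
|---|---|---|---|
| Table 8 average | 8.3 | 33.2/4 = 8.3 | – |
| Table 8 min | 6.6 | 30.0/4 = 7.5 | 6.6 |
| Table 8 max | 8.0 | 36.4/4 = 9.1 | 11.0 |
| Table 9 average | 8.5 | 42.7/5 = 8.54 | – |
| Table 9 min | 6.2 | 36.0/5 = 7.2 | 6.2 |
| Table 9 max | 11.0 | 53.4/5 = 10.68 | 11.4 |

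The average cells are right. The Min cells are true overall minima under a label that says average. Only the two Max cells fit neither definition. The 8.0 equals device 4's value, the smallest of the four maxima; the 11.0 in Table 9 equals the median and the last device row.

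**4. What the force test says about a projection without a loop**

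The loops were cut, so the lowest value, 6.6 N, is strength without the loop. Simulated-use retraction force (item c under device detachment) was 2.5 +/- 1 N. Taking the upper end as 2.5 + 1 = 3.5 N, the gap is 6.6 - 3.5 = 3.1 N. This sets a single-projection strength against a whole-device force in porcine colon; load per projection was not measured.

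**The case against.** The strongest reply is that the conflict is one of wording and leaves the safety case largely intact. Much of that stands.

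- A reader might infer that three projections can be lost by a single break. The documents do not establish this. The pictures of the loop and web are not available here, and the text hints at joins between projections: it speaks of webbed portions separating from each other, and says that in some cases even two breakages would not free a projection. Five may also be the misprint.
- A reader might infer that projections without a loop have neither redundancy nor a strength advantage. The protocol claims no strength advantage; it says only that the projections appear as robust as the comparator's. The averages of 8.3 and 8.5 N are its own correct figures. The difference in device averages is 8.30 - 8.54 = -0.24 N (Welch 95% CI -1.0 to +0.5, 4 versus 5 devices), and the NuView minimum of 6.6 N is above the comparator's 6.2 N. Correcting the Max cells changes none of this, and the Table 8 error understates the sponsor's own device.
- A reader might infer that the acceptable-risk conclusion falls. It also rests on the adverse-event database review, removal of the thin pin joint and the force tests, and the protocol notes that the comparator has no such loop.

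A duodenoscope examination follows NuView use, which offers some chance of seeing a fragment. Its stated purpose, however, is to confirm the view of the papilla, not to account for the device.

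What the reply does not remove is the contradiction itself. The missing pictures cannot make the sentences agree.

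**Conclusion.** The contradiction holds: redundancy is claimed for every projection in three places and for five in a fourth. If there are eight projections per device and five have the loop, up to three are not stated to have it. That count depends on item a being correct for the clinical build. The documents support a need to reconcile, not a finding that the device is unsafe. For any projection without a loop, the case would rest on the cut-loop test and the other listed controls, subject to the limits of comparing single-projection strength with a whole-device force.

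The table errors are minor. Two Max cells are wrong and two Min cells are mislabelled. The quoted averages and minima and the comparison with the Arc Endocuff do not change. The primary endpoint and its analysis are unaffected.

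**What to change.** 1. Check the loop count against the clinical build and make Table 4, the loop description, item a and item b agree.
2. If five of eight is right, limit the redundancy claim to the looped projections in Table 4, the loop description and item b. State that up to three are not covered, and rest the case for those on the cut-loop force test (minimum 6.6 N against 2.5 +/- 1 N on the whole device) and the other listed controls. Make the counseling text match.
3. Correct the summary rows. As column means they are 8.3 / 7.5 / 9.1 N (Table 8) and 8.5 / 7.2 / 10.7 N (Table 9). Alternatively, keep the minima, label the cells as overall minimum and maximum, and print 6.6 / 11.0 N and 6.2 / 11.4 N.
4. At section 3.1.6.2 step b item 6 and section 5.6 item f, add an inspection of the withdrawn NuView, confirm that all projections in the reconciled design count are present, and record the result.

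The cost is text edits, a brief check for each of three patients, and a slightly less favourable risk statement if five is confirmed.
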